2.2. Pooling Algorithm for Analysis Centers

This is a single center study; therefore, the pooling algorithm is not applicable.

2.3. Analysis Sets

The analysis sets consist of Safety analysis population and Pharmacokinetics (PK) analysis population.

2.3.1. Safety Analysis Set

Safety analysis population is defined as all subjects who received the study drug.

2.3.2. Pharmacokinetics Analysis Set

Pharmacokinetics (PK) analysis population is defined as all subjects receiving the study drug and having at least one plasma concentration data after administration

2.4. Definition of Subgroups

Not applicable.

2.5. Summary Statistics

Summary statistics for continuous variables are number of subjects, arithmetic mean (Mean), standard deviation (SD), median, minimum, and maximum.

In PK analysis, geometric mean (geo mean), coefficient of variation (CV %) and 90% confidence intervals of geo mean are also presented. The formulas for calculation are shown as following:

$$\text{Geometric mean} = \exp \left[\frac{\sum_{i=1}^n \log X_i}{n} \right] = \sqrt[n]{\prod_{i=1}^n X_i}$$

Refer to the current “Guideline for Analysis of Pharmacokinetic Data” for general rules for rounding values.

As for displaying the descriptive statistics in safety analysis, arithmetic mean and median are rounded to one more digit for display than what was used to collect the variable. SD is rounded to one more additional decimal place than that of mean. Minimum and maximum are the same number of digit for display used to collect the variable.

Categorical variables are summarized using frequency and percent. Percent is rounded to the nearest tenth.

2.6. Other Methodological Notes

Calculation for study day:

- Post-treatment study day: [The date of a respective event] – [The date of Prezcobix dose] +1
- Pre-treatment study day: [The date of a respective event during pre-dosing time] – [The date of first Prezcobix dose]

3. INTERIM ANALYSIS AND DATA MONITORING COMMITTEE REVIEW

Not applicable.

4. SUBJECT INFORMATION

4.1. Demographics and Baseline Characteristics

For the demographic parameters and baseline characteristics, descriptive statistics will be calculated for the continuous variables and the categorical variables will be presented using frequency and percent.

Demographic Parameters

- Age at the time of informed consent (years)
- Sex
- Ethnicity
- Race

- Country of Site
- Height (cm) at screening
- Weight (kg) at screening
- BMI (kg/m²)
* Body mass index (BMI) = weight (kg) / (height (m))²

Baseline Characteristics

- Medical History [Yes, No]
- Physical Examination [Clinically Significant, Not Clinically Significant]
* If a subject has at least one body system with clinically significant results, the subject will be counted as having clinically significant results.
- Complications [Yes, No]
- Cigarette Use [Current, Former, Never]

4.2. Disposition Information

Study completion/withdrawal information and evaluable subjects who are included in the analysis sets will be tabulated and listed.

4.3. Treatment Compliance

Not applicable.

4.4. Extent of Exposure

Study drug administration information will be reported in listings.

4.5. Protocol Deviations

All major protocol deviations will be displayed in a listing.

4.6. Prior and Concomitant Medications

Prior therapies and concomitant medications will be reported in listings.

5. EFFICACY

Efficacy analyses will not be conducted.

6. SAFETY

6.1. Adverse Events

All AEs will be coded using MedDRA version 20.0. All AEs and special reporting situations, whether serious or non-serious, will be reported from the time a signed and dated informed consent form (ICF) is obtained until completion of the subject's last study-related procedure (which may include contact for follow-up of safety).

All reported AEs that newly occurred after the administration of Prezcobix and those that worsened after the treatment are defined as treatment-emergent AEs (TEAE).

Adverse Event Associated with the Use of the Drug

An AE is considered associated with the use of the drug if the attribution is possible, probable, or very likely.

AEs will be summarized by preferred term (PT) per system organ class (SOC) and include number (and %) of subjects reporting any AEs. For each AE, the percentage of subjects who experience at least 1 occurrence of the given event will be summarized.

The incidence rates of AE are calculated as a percentage of the number of subjects with AEs in Safety Analysis Population.

$$\text{Incidence Rate (\%)} = \frac{\text{The Number of Subjects with AEs}}{\text{Safety Analysis Population}} \times 100$$

For number of subjects, each subject will contribute at most one count per summarization category.

For severity, each subject with more than one AE in the same SOC/PT will be counted once by using the highest intensity (Severe > Moderate > Mild).

For the relationship with the study drug, the latest events will be counted.

Tabulations will be provided for the following information. The number (and %) of subjects will be shown in all tables.

- AE preferred terms per body system organ class
- AE preferred terms per body system organ class by severity
- AE preferred terms per body system organ class by relationship to study drug

The following AE Listings will be provided.

- All AEs
- Death
- Serious AEs without death

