11.4. Safety Analyses

All subjects who received the study drug will be included in the safety and tolerability analysis. Baseline for all laboratory evaluations and vital signs will be defined as the last evaluation done before the first study drug administration. Safety will be evaluated by examining frequency, severity and type of AEs, and changes in clinical laboratory test values, physical examination results, vital signs and ECG measurements.

AEs

The verbatim terms used in the CRF by investigators to identify AEs will be coded using the Medical Dictionary for Regulatory Activities (MedDRA). All reported AEs with onset during the treatment phase (ie, treatment-emergent AEs, and AEs that have worsened since baseline) will be included in the analysis. For each AE, the percentage of subjects who experience at least 1 occurrence of the given event will be summarized.

Summaries, listings, datasets, or subject narratives may be provided, as appropriate, for those subjects who die, who discontinue treatment due to an AE, or who experience a severe or a serious adverse event (SAE).

Clinical Laboratory Tests

Laboratory data will be summarized by type of laboratory test. Normal ranges and markedly abnormal results (specified in the Statistical Analysis Plan) will be used in the summary of laboratory data. Descriptive statistics will be calculated for each laboratory analyte at baseline and at each scheduled time point. Changes from baseline results will be presented in preversus posttreatment cross-tabulations (with classes for below, within, and above normal ranges). A listing of subjects with any laboratory results outside the reference ranges will be provided. A listing of subjects with any markedly abnormal laboratory results will also be provided.

Electrocardiogram (ECG)

All clinically relevant abnormalities in ECG wave form that are changes from the baseline readings will be reported (eg, changes in T-wave morphology or the occurrence of U-waves).

Vital Signs

Descriptive statistics of temperature, pulse/heart rate, respiratory rate, and blood pressure (systolic and diastolic, supine position) values and changes from baseline will be summarized at each scheduled time point.

The percentage of subjects with values beyond clinically important limits will be summarized.

Physical Examination

Physical examination findings and changes from baseline will be summarized at each scheduled time point.

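### SAP 6.1 counts drug relationship by the latest event, at an unstated level, so the drug-associated subject count can fall below the number who had such an event

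*SAP*

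**What the plan says.** SAP 6.1 sets three counting rules for AE tables.

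- General: "For number of subjects, each subject will contribute at most one count per summarization category".
- Severity: "each subject with more than one AE in the same SOC/PT will be counted once by using the highest intensity".
- Relationship: "For the relationship with the study drug, the latest events will be counted". No level and no reason are given.

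The same section defines the drug-associated class: "An AE is considered associated with the use of the drug if the attribution is possible, probable, or very likely". It plans a table titled "AE preferred terms per body system organ class by relationship to study drug", with number and percentage of subjects. The denominator comes from SAP 2.3.1: "Safety analysis population is defined as all subjects who received the study drug".

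The protocol has no rule that would override the relationship sentence. Section 11.4 states "Safety will be evaluated by examining frequency, severity and type of AEs", together with changes in laboratory tests, examinations, vital signs and ECG. It is silent on how relationship is counted. Protocol 12.1.2 defines five attribution levels.

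**The concern.** The usual reader of a relationship table wants to know how many subjects had at least one event that the investigator attributed to the drug. A latest-event rule answers a different question: how the subject's last event in that row was attributed. The two answers differ whenever a drug-associated event is followed by an unrelated one, and they always differ in the same direction.

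Safety is the secondary objective, and the relationship table is one of three planned AE tabulations. A subject with a drug-associated event could be missing from the drug-associated figure, and the table would give no sign of it.

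**Working it through.** The plan states no figure for this rule, so there is none to reproduce. The check compares the latest-event rule with a strongest-relationship rule.

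**Inputs.** 8 planned subjects (SAP 1.4), all assumed dosed. Drug-associated means possible, probable or very likely (SAP 6.1); the other two levels are doubtful and not related (Protocol 12.1.2).

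**Direction.** For subject i in a given row, let L = 1 if the latest event is drug-associated and A = 1 if any event is. The latest event is one of the events, so L ≤ A for every subject. Summed over subjects, the latest-event count is at most the count with at least one drug-associated AE.

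**Size per subject.** 1/8 = 12.5%. If replacements bring the dosed number to 9, 1/9 = 11.1%.

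**Example with two PTs.** One subject has nausea judged possible on Day 1 and diarrhea judged not related on Day 6. Protocol Section 8 foresees both events and Attachment 1 groups both as gastrointestinal; that they share a MedDRA SOC is an assumption. Drug-associated totals, with latest applied separately at each level:

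| Row | Latest event | Strongest relationship |
|---|---|---|
| Nausea (PT) | 1/8 (12.5%) | 1/8 (12.5%) |
| Diarrhea (PT) | 0/8 | 0/8 |
| SOC | 0/8 | 1/8 (12.5%) |
| Overall, if shown | 0/8 | 1/8 (12.5%) |

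If both events had been nausea, the PT row would also show 0/8 under the latest-event rule and 1/8 under the other.

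**Enumeration.** Take two ordered events in one SOC with two PTs, each event associated or not: (2 × 2)² = 16 patterns, of which 12 contain a drug-associated event.

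| Rule | SOC total understated | SOC total below a PT total |
|---|---|---|
| Latest, applied at SOC level | 4 | 2 |
| Latest within PT, SOC built from its PTs | 2 | 0 |
| Strongest relationship | 0 | 0 |

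These are counts of patterns, not probabilities. Understatement survives either choice of level. A SOC total below its PT total needs latest to be applied at SOC level.

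**Other reading.** If the sentence means the latest assessment of one event, it resolves updates to that event only. For the subject in the example, whose two events have different attributions, the SAP would then give no rule for the SOC row.

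**The case against.** The strongest objection is that the sentence is ambiguous rather than harmful. It may refer to the latest assessment of an event, in which case nothing is understated. That reading is possible, but it leaves the several-events case without a rule, so the sentence needs changing either way.

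A second objection is that little is at stake. The study is descriptive, with a single dose and 8 planned subjects. The SAP plans a listing of all AEs, and Protocol 12.3.1 has the investigator record the relationship of each AE in the CRF, so anyone can recount. The overall AE table is unaffected. This stands and limits the materiality, although the relationship table itself would still be uncorrected.

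Three stronger readings are tempting but not supported.

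- A reader might infer that SOC rows will generally fall below their PT rows, and that the severity rule is free of this. The SAP does not say whether the table shows five attribution rows or a collapsed drug-associated total. In single-category rows the mismatch arises under any one-count rule: two events in different PTs at different attribution levels give it in 5 × 4 = 20 of 25 ordered patterns, under the latest-event and strongest-relationship rules alike. Severity behaves the same way: one Mild event in one PT and one Moderate in another leave the SOC Mild row at 0. The anomaly described above concerns only a collapsed drug-associated total with latest applied at SOC level, a level that the relationship sentence does not state.
- A reader might infer a conflict with the protocol. Protocol 11.4 has no relationship counting rule to conflict with.
- A reader might infer that drug-related events will in fact be hidden, because later events lie further from a single dose and the attribution definitions use timing. That direction is plausible, but the documents give no rate for subjects with mixed attributions, so no probability can be attached.

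**Conclusion.** The point holds as a defect of a stated rule, with low materiality. On the natural reading, the rule can only lower the drug-associated count or leave it unchanged, by 12.5 percentage points per affected subject among 8. It takes effect only if a subject has at least two AEs of differing attribution in one row, with the drug-associated one earlier; this may never happen in the study. A SOC total below its own PT total is a further possibility under two conditions: latest is applied at SOC level, and a collapsed drug-associated total is shown. On the alternative reading, the finding becomes a missing rule for subjects whose events have different attributions.

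**What to change.** Replace the relationship sentence in SAP 6.1 with wording such as: *A subject with more than one AE in a PT, SOC or overall row is counted once at the strongest relationship (very likely > probable > possible > doubtful > not related). If the attribution of a single event is updated, the investigator's final assessment of that event is used.*

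This states the level, covers several events per subject, and keeps the legitimate use of a latest value, which is an update to one event. It is a change of SAP wording and of the matching table program, with no new data. The one downside is that the drug-related percentage may be slightly higher than under the present rule.

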6.2. Clinical Laboratory Tests

Laboratory parameters will be summarized and graphically presented. The parameters of interest, units, and ranges are as follows:

Hematology Panel

Parameter	Unit	Normal Range
Hemoglobin	g/dL	Male: 13.5 - 17.5, Female: 11.5 - 15.0
Hematocrit	%	Male: 39.7 - 52.4, Female: 34.8 - 45.0
Red Blood Cell (RBC) Count	$\times 10^4/\mu\text{L}$	Male: 430 - 570, Female: 380 - 500
Mean Corpuscular Hemoglobin (MCH)	pg	28.0 - 34.0
MCH Concentration (MCHC)	%	30.2 - 35.1
Mean Corpuscular Volume (MCV)	fL	85 - 102
White Blood Cell (WBC) Count	/uL	3300- 9000
Basophils/Leukocytes	%	0.0 - 2.0
Eosinophils/Leukocytes	%	0.0 - 8.0
Lymphocytes/Leukocytes	%	18.0 - 49.0
Monocytes/Leukocytes	%	2.0 - 10.0
Neutrophils/Leukocytes	%	40.0 - 75.0
Platelet Count	$\times 10^4/\mu\text{L}$	14.0 - 34.0

Serum Chemistry Panel

Parameter	Unit	Normal Range
Sodium	mEq/L	137 - 147
Potassium	mEq/L	3.5 - 5.0
Chloride	mEq/L	98 - 108
Blood Urea Nitrogen (BUN)	mg/dL	8.0 - 20.0
Creatinine	mg/dL	Male: 0.61 - 1.04, Female: 0.47 - 0.79
Glucose	mg/dL	70 - 109
Aspartate Aminotransferase (AST)	U/L	10 - 40
Alanine Aminotransferase (ALT)	U/L	5 - 45
Gamma-glutamyltransferase (GGT)	U/L	Male: ≤80, Female: ≤30
Total Bilirubin	mg/dL	0.2 - 1.2
Direct Bilirubin	mg/dL	0.0 - 0.2
Indirect Bilirubin	mg/dL	0.2 - 1.0
Creatinine Clearance (Ccr)	mL/min	70≤
Alkaline Phosphatase (ALP)	U/L	100 - 325
Creatinine Phosphokinase (CPK)	U/L	Male: 60 - 270, Female: 40 - 150
Lactic Acid Dehydrogenase (LDH)	U/L	120 - 240
Uric Acid	mg/dL	Male: 3.8 - 7.0, Female: 2.5 - 7.0
Calcium (corrected for albumin)	mg/dL	8.4 - 10.4
Phosphate	mg/dL	2.5 - 4.5
Serum Albumin	g/dL	3.8 - 5.2
Total Protein	g/dL	6.7 - 8.3
Total Cholesterol	mg/dL	120 - 219
High-density Lipoprotein (HDL) Cholesterol	mg/dL	Male: 40 - 85, Female: 40 - 95
Low-density Lipoprotein (LDL) Cholesterol	mg/dL	65 - 139
Triglycerides	mg/dL	30 - 149
Magnesium	mg/dL	1.9 - 2.5

Urinalysis

Parameter		Unit	Normal Range	Values
Dipstick	pH		5.0 - 7.5	
	Glucose		-	-, 1+, 2+, 3+, 4+
	Protein		-	-, +-, 1+, 2+, 3+
	Blood		-	-, +-, 1+, 2+, 3+
	Ketones		-	-, +-, 1+, 2+, 3+
Sediment	RBC	/HPF	≤4	<1, 1-4, 5-9, 10-19, 20-29, 30-49, 50-99, ≥100
	WBC	/HPF	≤4	<1, 1-4, 5-9, 10-19, 20-29, 30-49, 50-99, ≥100
	Squamous Epithelial Cell	/HPF	≤4	<1, 1-4, 5-9, 10-19, 20-29, 30-49, 50-99, ≥100
Specific gravity			1.006 - 1.030	

For Laboratory parameters marked abnormal limits are defined as follows:

Hematology Panel

	Grade 1 Mild	Grade 2 Moderate	Grade 3 Severe	Grade 4 Potentially Life-Threatening
Hemoglobin ¹ , Low (g/dL; mmol/L) ² ≥13 years of age (male only)	10.0 to 10.9 6.19 to 6.76	9.0 to <10.0 5.57 to <6.19	7.0 to <9.0 4.34 to <5.57	<7.0 <4.34
Hemoglobin ¹ , Low (g/dL; mmol/L) ² ≥13 years of age (female only)	9.5 to 10.4 5.88 to 6.48	8.5 to <9.5 5.25 to <5.88	6.5 to <8.5 4.03 to <5.25	<6.5 <4.03
Absolute Lymphocyte Count, Low (cell/mm ³ ; cells/L) >5 years of age (not HIV infected)	600 to <650 0.600 x 10 ⁹ to <0.650 x 10 ⁹	500 to <600 0.500 x 10 ⁹ to <0.600 x 10 ⁹	350 to <500 0.350 x 10 ⁹ to <0.500 x 10 ⁹	<350 <0.350 x 10 ⁹
Platelets, Decreased (cells/mm ³ ; cells/L)	100,000 to <124,999 100,000 x 10 ⁹ to <124,999 x 10 ⁹	50,000 to <100,000 50,000 x 10 ⁹ to <100,000 x 10 ⁹	25,000 to <50,000 25,000 x 10 ⁹ to <50,000 x 10 ⁹	<25,000 <25,000 x 10 ⁹
WBC, Decreased (cells/mm ³ ; cells/L) >7 days of age	2,000 to 2,499 2.000 x 10 ⁹ to 2.499 x 10 ⁹	1,500 to 1,999 1.500 x 10 ⁹ to 1.999 x 10 ⁹	1,000 to 1,499 1.000 x 10 ⁹ to 1.499 x 10 ⁹	<1,000 <1.000 x 10 ⁹

1: Male and female sex are defined as sex at birth.

2: The conversion factor used to convert g/dL to mmol/L is 0.6206 and is the most commonly used conversion factor. For grading hemoglobin results obtained by an analytic method with a conversion factor other than 0.6206, the result must be converted to g/dL using the appropriate conversion factor for the particular laboratory.

Serum Chemistry Panel

	Grade 1 Mild	Grade 2 Moderate	Grade 3 Severe	Grade 4 Potentially Life-Threatening
Albumin, Low (g/dL; g/L)	3.0 to <LLN 30 to <LLN	≥2.0 to <3.0 ≥20 to <30	<2.0 <20	NA
Alkaline Phosphatase, High	1.25 to <2.5 x ULN	2.5 to <5.0 x ULN	5.0 to <10.0 x ULN	≥10.0 x ULN
ALT or SGPT, High Report only one	1.25 to <2.5 x ULN	2.5 to <5.0 x ULN	5.0 to <10.0 x ULN	≥10.0 x ULN
AST or SGOT, High Report only one	1.25 to <2.5 x ULN	2.5 to <5.0 x ULN	5.0 to <10.0 x ULN	≥10.0 x ULN
Direct Bilirubin ³ , High >28 days of age	NA	NA	>ULN	>ULN with life-threatening consequences (e.g., signs and symptoms of liver failure)
Total Bilirubin, High >28 days of age	1.1 to <1.6 x ULN	1.6 to <2.6 x ULN	2.6 to < 5.0 x ULN	≥5.0 x ULN
Calcium, High (mg/dL; mmol/L) ≥7 days of age	10.6 to <11.5 2.65 to <2.88	11.5 to <12.5 2.88 to <3.13	12.5 to <13.5 3.13 to <3.38	≥13.5 ≥3.38
Calcium, Low (mg/dL; mmol/L) ≥7 days of age	7.8 to <8.4 1.95 to <2.10	7.0 to <7.8 1.75 to <1.95	6.1 to <7.0 1.53 to <1.75	<6.1 <1.53
Creatine Kinase, High	3 to <6 x ULN	6 to <10 x ULN	10 to <20 x ULN	≥20 x ULN
Creatinine, High	1.1 to 1.3 x ULN	>1.3 to 1.8 x ULN OR Increase of >0.3 mg/dL above baseline	>1.8 to <3.5 x ULN OR Increase of 1.5 to <2.0 x above baseline	≥3.5 x ULN OR Increase of ≥2.0 x above baseline
Creatinine Clearance ⁴ or eGFR, Low Report only one	NA	<90 to 60 ml/min or ml/min/1.73 m ² OR 10 to <30% decrease from baseline	<60 to 30ml/min or ml/min/1.73 m ² OR ≥30 to <50% decrease from baseline	<30 ml/min or ml/min/1.73 m ² OR ≥50% decrease from baseline or dialysis needed
Glucose (mg/dL; mmol/L) Fasting, High Nonfasting, High	110 to 125 6.11 to <6.95	>125 to 250 6.95 to <13.89	>250 to 500 13.89 to <27.75	>500 ≥27.75
Glucose, Low (mg/dL; mmol/L) ≥1 month of age	55 to 64 3.05 to 3.55	40 to <55 2.22 to <3.05	30 to <40 1.67 to <2.22	<30 <1.67
Magnesium ⁵ , Low (mEq/L; mmol/L)	1.2 to <1.4 0.60 to <0.70	0.9 to <1.2 0.45 to <0.60	0.6 to <0.9 0.30 to <0.45	<0.6 <0.30
Phosphate, Low (mg/dL; mmol/L) >14 years of age	2.0 to < LLN 0.81 to < LLN	1.4 to < 2.0 0.65 to < 0.81	1.0 to <1.4 0.32 to <0.65	<1.0 <0.32
Potassium, High (mEq/L; mmol/L)	5.6 to <6.0 5.6 to <6.0	6.0 to <6.5 6.0 to <6.5	6.5 to <7.0 6.5 to <7.0	≥7.0 ≥7.0

	Grade 1 Mild	Grade 2 Moderate	Grade 3 Severe	Grade 4 Potentially Life-Threatening
Potassium, Low (mEq/L; mmol/L)	3.0 to <3.4 3.0 to <3.4	2.5 to <3.0 2.5 to <3.0	2.0 to <2.5 2.0 to <2.5	<2.0 <2.0
Sodium, High (mEq/L; mmol/L)	146 to <150 146 to <150	150 to <154 150 to <154	154 to <160 154 to <160	≥160 ≥160
Sodium, Low (mEq/L; mmol/L)	130 to <135 130 to <135	125 to <130 125 to <135	121 to <125 121 to <125	≤120 ≤120
Uric Acid, High (mg/dL; mmol/L)	7.5 to <10.0 0.45 to <0.59	10.0 to <12.0 0.59 to <0.71	12.0 to <15.0 0.71 to <0.89	≥15.0 ≥0.89

3: Direct bilirubin >1.5 mg/dL in a participant <28 days of age should be graded as grade 2, if <10% of the total bilirubin.

4: Use the applicable formula (Cockcroft-Gault in mL/min or Schwartz in mL/min/1.73m²).

5: To convert a magnesium value from mg/dL to mmol/L, laboratories should multiply by 0.4114.

Urinalysis

	Grade 1 Mild	Grade 2 Moderate	Grade 3 Severe	Grade 4 Potentially Life-Threatening
Glycosuria (random collection tested by dipstick)	Trace to 1+ or ≤250 mg	2+ or >250 to ≤500 mg	>2+ or >500 mg	NA
Proteinuria (random collection tested by dipstick)	1+	2+	3+ or higher	NA

Baseline laboratory evaluations are defined as the last evaluation done before the study drug administration.

On-treatment evaluations will be those performed after the study drug administration to the completion of study/withdrawal date.

The following analyses will be performed. Tables and figures:

For continuous parameters (hematology, biochemistry, and pH, specific gravity in urinalysis):

- Descriptive statistics at each scheduled time point on actual value and changes from baseline. (Use the analysis time points defined in [2.1](#))
- Shift from pre- versus post-treatment cross-tabulations (with classes for low, normal, high ranges and using the analysis time points defined in [2.1](#))
- Line plots of individual observed values at each scheduled time point (Use all the time points observed)
- Line plots of Mean and SD at each scheduled time point (Use the analysis time points defined in [2.1](#))

For qualitative parameters (urinalysis except for pH and specific gravity):

- Tabulation of baseline and values at each scheduled time point (Use the analysis time points defined in 2.1)
- Shift from pre- versus post-treatment cross-tabulations and using the analysis time points defined in 2.1)

The following analyses will be performed. Listing:

- Listing of subjects with laboratory results
- Listing of subjects with any laboratory results outside the normal range
- Listing of subjects with any markedly abnormal laboratory results

